Immunodeficiencies of interest	Comorbidity	Defined as ≥1 ICD-10 diagnosis code for immunodeficiency. Complete list in ANNEX 5. LIST OF DIAGNOSIS CODES FOR SELECT IMMUNODEFICIENCIES OF INTEREST.
Prior use of corticosteroids	Medication history	Defined as ≥1 prescription dispensing of a corticosteroid (as identified by ATC code[s]) in the 12 months prior to the index tofacitinib dispensing. Complete list in ANNEX 4. LIST OF ATC CODES FOR COMEDICATIONS OF INTEREST
Prior use of statins	Medication history	Defined as ≥1 prescription dispensing of a statin (as identified by ATC code[s]) in the 12 months prior to the index tofacitinib dispensing. Complete list in ANNEX 4. LIST OF ATC CODES FOR COMEDICATIONS OF INTEREST.

Table 3. Operational definitions of study variables in Système National des Données de Santé

Variable	Role	Operational definition
Prior use of any biologic	Medication history	Defined as ≥1 prescription dispensing of a biologic (as identified by ATC code[s]) in the 12 months prior to the index tofacitinib dispensing. Complete list in ANNEX 7. LIST OF ATC CODES FOR MEDICATIONS OF INTEREST TO AVOID WHILE TAKING TOFACITINIB.
Prior use of conventional synthetic DMARDs (csDMARDs)/ Immunomodulators	Medication history	Defined as ≥1 prescription dispensing of a csDMARD/ Immunomodulators (as identified by ATC code[s]) in the 12 months prior to the index tofacitinib dispensing. Complete list in ANNEX 7. LIST OF ATC CODES FOR MEDICATIONS OF INTEREST TO AVOID WHILE TAKING TOFACITINIB.
Prior use of MTX	Medication history	Defined as ≥1 prescription dispensing of MTX (as identified by ATC code L04AX03) in the 12 months prior to the index tofacitinib dispensing.
Prior use of anti-TB therapy	Medication history	Defined as ≥1 prescription dispensing of anti-TB therapy (as identified by ATC code[s]) in the 12 months prior to the index tofacitinib dispensing.
Prior vaccination	Medication history	Defined as ≥1 procedure code, ≥1 ICD-10 code and/or ≥1 reimbursed prescription (as identified by ATC code[s]) for a vaccination, overall and stratified by live and non-live vaccinations (if available) in the 12 months prior to the index tofacitinib dispensing. Complete list in ANNEX 4. LIST OF ATC CODES FOR COMEDICATIONS OF INTEREST.

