History of	Outcome: changes	Defined as ≥1 ICD-10 diagnosis code for hypertension or ≥1
hypertension	in use in patients	prescription dispensing (as identified by ATC code[s]) for an
	with CV risk	antihypertensive in the 12 months prior to the index
	factors	tofacitinib dispensing. Complete list in ANNEX 8. LIST OF
		ATC CODES FOR ANTIHYPERTENSIVES.

¹ Potential for very low sensitivity leading to misclassification. This variable will be reported if feasible

Table 3. Operational definitions of study variables in Système National des Données de Santé

Variable	Role	Operational definition
History of chronic kidney disease	Outcome: changes in use in patients with CV risk factors	Defined as ≥1 ICD-10 diagnosis code for chronic kidney disease in the 12 months prior to the index tofacitinib dispensing.
CV risk factor scores	Outcome: changes in use in patients with CV risk factors	Calculated as the sum of the number of CV risk factors (as listed and defined above) identified in the 12 months prior to the index tofacitinib dispensing. Weighting of CV risk factors may be considered as a sensitivity analysis to reflect the potential different importance of each risk factor.
Initiating tofacitinib with ≥1 CV risk factor (s)	Outcome: changes in use in patients with CV risk factors	Defined as ≥1 CV risk factor(s) (as listed and defined above) identified in the 12 months prior to the index tofacitinib dispensing (unless otherwise specified).
Initiating tofacitinib with ≥1 CV risk factor and no prior use of an alternative therapy (i.e., biologic)	Outcome: changes in use in patients with CV risk factors	Defined as ≥1 CV risk factor (as listed and defined above) identified in the 12 months prior to the day of the index tofacitinib dispensing and 0 prescription medication dispensing for an alternative therapy (i.e., biologic) in the 12 months prior to the date of the index tofacitinib prescription dispensing. Complete list of biologics in ANNEX 7. LIST OF ATC CODES FOR MEDICATIONS OF INTEREST TO AVOID WHILE TAKING TOFACITINIB.
Assessment of CV risk for versus < 65 years))	actors while receiving	tofacitinib therapy (will be stratified by sex and age (≥65 years

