Hyperlipidaemia	Outcome: changes in use in patients with CV risk factors	Defined as ≥1 ICD-10 diagnosis code for hyperlipidaemia or ≥1 prescription dispensing (as identified by ATC code[s]) for a statin or other antihyperlipidaemic while receiving tofacitinib. Complete list in ANNEX 9. LIST OF ATC CODES FOR ANTIHYPERLIPIDAEMICS.
Age ≥65 years	Outcome: changes in use in patients with CV risk factors	Defined as age ≥65 years while receiving tofacitinib.
Current smoker	Outcome: changes in use in patients with CV risk factors	Defined as ≥1 ICD-10 diagnosis code for tobacco use disorder or ≥1 procedure code for counselling visits for smoking or ≥1 prescription dispensing (as identified by ATC code[s]) for a nicotine replacement product while receiving tofacitinib.
Coronary artery disease (defined as MI, stroke, CABG or PCI)	Outcome: changes in use in patients with CV risk factors	Defined as ≥1 ICD-10 diagnosis code for MI or stroke or ≥1 procedure code for CABG or PCI while receiving tofacitinib therapy.

Table 3. Operational definitions of study variables in Système National des Données de Santé

Variable	Role	Operational definition
Stable angina pectoris	Outcome: changes	Defined as ≥1 ICD-10 diagnosis code for stable angina
8 ₁	in use in patients	pectoris while receiving tofacitinib therapy.
	with CV risk	
	factors	
Diabetes	Outcome: changes	Defined as ≥1 ICD-10 diagnosis code for diabetes while
	in use in patients	receiving tofacitinib therapy.
	with CV risk	
	factors	
Hypertension	Outcome: changes	Defined as ≥1 ICD-10 diagnosis code for hypertension or ≥1
	in use in patients	prescription dispensing (as identified by ATC code[s]) for an
	with CV risk	antihypertensive while receiving tofacitinib.
	factors	Complete list in ANNEX 8. LIST OF ATC CODES FOR
		ANTIHYPERTENSIVES.
Chronic kidney	Outcome: changes	Defined as ≥1 ICD-10 diagnosis code for chronic kidney
disease	in use in patients	disease while receiving tofacitinib.
	with CV risk	
Discontinuation of	factors	Defined as >1 CV misk featon(a) while massiving tofesitinih
tofacitinib after	Outcome: changes	Defined as ≥1 CV risk factor(s) while receiving to facitinib therapy (as listed and defined above) plus 0 prescription
	in use in patients with CV risk	dispensing for tofacitinib within a specific time window after
developing ≥1 CV risk factors while taking	factors	the code for the first CV risk factor.
tofacitinib	Tactors	the code for the first C v fisk factor.

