ANNEX 4. LIST OF ATC CODES FOR COMEDICATIONS OF INTEREST

All codes will be reviewed and updated prior to study initiation.

Class of drug	Drug	ATC code
Corticosteroids	Aldosterone	H02AA01
	Fludrocortisone	H02AA02
	Desoxycortone	H02AA03
	Betamethasone	H02AB01
	Dexamethasone	H02AB02
	Fluocortolone	H02AB03
	Methylprednisolone	H02AB04
	Paramethasone	H02AB05
	Prednisolone	H02AB06
	Prednisone	H02AB07
	Triamcinolone	H02AB08
	Hydrocortisone	H02AB09 (D07XA01 topical
		use)
	Cortisone	H02AB10
	Prednylidene	H02AB11
	Rimexolone	H02AB12
	Deflazacort	H02AB13
	Cloprednol	H02AB14
	Meprednisone	H02AB15
	Cortivazol	H02AB17
	Methylprednisolone, combinations	H02BX01
	Trilostane	H02CA01
	Phenylbutazone and corticosteroids	M01BA01
	Dipyrocetyl and corticosteroids	M01BA02
	Acetylsalicylic acid and corticosteroids	M01BA03
Methotrexate	Methotrexate	L04AX03
Statins	Atorvastatin	C10AA05
	Atorvastatin and acetylsalicylic acid	C10BX08
	Atorvastatin and amlodipine	C10BX03
	Atorvastatin and ezetimibe	C10BA05
	Atorvastatin and perindopril	C10BX15
	Atorvastatin, acetylsalicylic acid and perindopril	C10BX12
	Atorvastatin, acetylsalicylic acid and ramipril	C10BX06
	Atorvastatin, amlodipine and perindopril	C10BX11
	Cerivastatin	C10AA06
	Fluvastatin	C10AA04
	Gemigliptin and rosuvastatin	A10BH52
	Imipenem and cilastatin	J01DH51
	Lovastatin	C10AA02
	Lovastatin and nicotinic acid	C10BA01
	Nystatin	A07AA02, D01AA01, G01AA01
	Nystatin, combinations	G01AA51
	Pentostatin	L01XX08
	Pitavastatin	C10AA08
	Pravastatin	C10AA03
	Pravastatin and acetylsalicylic acid	C10BX02

PFIZER CONFIDENTIAL

Class of drug	Drug	ATC code
	Pravastatin and fenofibrate	C10BA03
	Rosuvastatin	C10AA07
	Rosuvastatin and acetylsalicylic acid	C10BX05
	Rosuvastatin and amlodipine	C10BX09
	Rosuvastatin and ezetimibe	C10BA06
	Rosuvastatin and valsartan	C10BX10
	Rosuvastatin, amlodipine and lisinopril	C10BX07
	Rosuvastatin, amlodipine and perindopril	C10BX14
	Rosuvastatin, perindopril and indapamide	C10BX13
	Simvastatin	C10AA01
	Simvastatin and acetylsalicylic acid	C10BX01
	Simvastatin and ezetimibe	C10BA02
	Simvastatin and fenofibrate	C10BA04
	Simvastatin, acetylsalicylic acid and ramipril	C10BX04
	Sitagliptin and simvastatin	A10BH51
Vaccinations	Anthrax antigen	J07AC01
	Brucella antigen	J07AD01
	Cholera, inactivated, whole cell	J07AE01
	Cholera, live attenuated	J07AE02
	Cholera, combinations with typhoid vaccine,	J07AE51
	inactivated, whole cell	
	Diphtheria toxoid	J07AF01
	Haemophilus influenzae B, purified antigen	J07AG01

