ANNEX 9. LIST OF ATC CODES FOR ANTIHYPERLIPIDAEMICS

All codes will be reviewed and updated prior to study initiation.

Class of drug	Drug	ATC code
Lipid modifying agents, plain	Simvastatin	C10AA01
	Lovastatin	C10AA02
	Pravastatin	C10AA03
	Fluvastatin	C10AA04
	Atorvastatin	C10AA05
	Cerivastatin	C10AA06
	Rosuvastatin	C10AA07
	Pitavastatin	C10AA08
	Clofibrate	C10AB01
	Bezafibrate	C10AB02
	Aluminium clofibrate	C10AB03
	Gemfibrozil	C10AB04
	Fenofibrate	C10AB05
	Simfibrate	C10AB06
	Ronifibrate	C10AB07
	Ciprofibrate	C10AB08
	Etofibrate	C10AB09
	Clofibride	C10AB10
	Choline fenofibrate	C10AB11
	Clofibrate	C10AB01
	Colestyramine	C10AC01
	Colestipol	C10AC02
	Colextran	C10AC03
	Colesevelam	C10AC04
	Niceritrol	C10AD01
	Nicotinic acid	C10AD02
	Nicofuranose	C10AD03
	Aluminium nicotinate	C10AD04
	Nicotinyl alcohol (pyridylcarbinol)	C10AD05
	Acipimox	C10AD06
	Nicotinic acid, combinations	C10AD52
	Dextrothyroxine	C10AX01
	Probucol	C10AX02
	Tiadenol	C10AX03
	Meglutol	C10AX05
	Omega-3-triglycerides incl. other esters and	C10AX06
	acids	
	Magnesium pyridoxal 5-phosphate glutamate	C10AX07
	Policosanol	C10AX08
	Ezetimibe	C10AX09
	Alipogene tiparvovec	C10AX10
	Mipomersen	C10AX11
	Lomitapide	C10AX12
	Evolocumab	C10AX13
	Alirocumab	C10AX14
	Bempedoic acid	C10AX15

Tofacitinib (Xeljanz®) A3921403 NON-INTERVENTIONAL STUDY PROTOCOL Protocol version 4.0, 26 February 2024

Class of drug	Drug	ATC code
	Inclisiran	C10AX16
	Evinacumab	C10AX17
	Volanesorsen	C10AX18

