Hypertension	Defined as ≥1 ICD-10 diagnosis code for hypertension or at least 3 reimbursements (or at least 2 in case of large pack sizes) of antihypertensive in the 12 months prior to or on the day of the index tofacitinib dispensing.	I10-I15
Prior myocardial infarction	Defined as ≥1 ICD-10 diagnosis code for a myocardial infarction in the 3 months prior to or on the day of the index tofacitinib dispensing.	I20-I25
Heart failure	Defined as ≥1 ICD-10 diagnosis code for heart failure in the 12 months prior to or on the day of the index tofacitinib dispensing.	I50, I110, I130 and I132
Inherited coagulation disorder	Defined as ≥1 ICD-10 diagnosis code for inherited coagulation disorder while receiving tofacitinib therapy.	D680, D681, D682, D66, D67, D689 and D686
Coronary heart disease	Defined as ≥1 ICD-10 diagnosis code for coronary heart disease.	I20-I25, I77 and Z95
Stable angina pectoris	Defined as ≥1 ICD-10 diagnosis code for stable angina pectoris.	I208 and I209
Hypercholesterolemia or dyslipidaemia or atherosclerosis	Defined as ≥1 ICD-10 diagnosis code for hypercholesterolemia or dyslipidaemia or atherosclerosis and ATC codes LLTs (statins, fibrates etc).	ICD-10: E780, E782, E783, E784, E785, E788, E789, Z863 and I70 ATC codes Statins: C10BA05, C10AA04 C10AA02, C10AA08, C10AA03, C10AA07 and C10AA01 ATC codes Fibrates: C10AB
Epstein-Barr virus (EBV)	Defined as ≥1 ICD-10 diagnosis code for Epstein-Barr virus.	D823, B348, B270, P358 and Z228
Hepatitis B virus (HBV)	Defined as ≥1 ICD-10 diagnosis code for Hepatitis B virus.	B181
Human papillomavirus (HPV)	Defined as ≥1 ICD-10 diagnosis code for HPV.	A630

Comorbidity	Definition	Codes (ICD-10 codes, ATC codes, CCAM procedure codes)
Human T-cell lymphotropic virus (HTLV)	Defined as ≥1 ICD-10 diagnosis code for human T-cell lymphotropic virus.	Z226, L303, B333 and B973
Hepatitis C virus (HCV)	Defined as ≥1 ICD-10 diagnosis code for hepatitis C virus.	B182 and B171
Coronary artery procedures*	Replacement of the ascending thoracic aorta and horizontal aorta with aortic valve replacement, with reimplantation of the coronary arteries, by thoracotomy with extracorporeal circulation	CCAM procedure code: DGKA014
	Ascending thoracic aorta replacement without aortic valve replacement, with coronary artery reimplantation, by thoracotomy with extracorporeal circulation	CCAM procedure code: DGKA003

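### Applied unrevised, Annex 9 would miss hyperlipidaemia treated only with a fixed statin combination; Annex 4 also lists six non-statin codes as statins, and Annex 11 gives a third list

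*Protocol*

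**What the plan says.** Three annexes of the protocol list statin codes, and Table 3 (Section 9.3.1) relies on them.

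- **Hyperlipidaemia as a CV risk factor.** Table 3 accepts one ICD-10 code or one dispensing, both before and during treatment. The on-treatment entry reads: "for a statin or other antihyperlipidaemic while receiving tofacitinib. Complete list in ANNEX 9. LIST OF ATC CODES FOR ANTIHYPERLIPIDAEMICS". The baseline entry also points to Annex 9. Annex 9 has a single class, "Lipid modifying agents, plain".
- **Prior use of statins.** Under Primary Objective 1, Table 3 has: "Defined as ≥1 prescription dispensing of a statin (as identified by ATC code[s]) in the 12 months prior to the index tofacitinib dispensing". It names Annex 4 as the complete list. Under Statins, Annex 4 includes combinations such as "Atorvastatin and ezetimibe" (C10BA05). It also includes "Imipenem and cilastatin" (J01DH51), nystatin ("A07AA02, D01AA01, G01AA01"), nystatin combinations (G01AA51) and pentostatin (L01XX08).
- **Annex 11.** The entry for hypercholesterolaemia, dyslipidaemia or atherosclerosis supplies the ICD-10 codes for this factor. Its statin codes are C10BA05, C10AA04 and then "C10AA02, C10AA08, C10AA03, C10AA07 and C10AA01". The definition joins diagnosis and ATC codes with *and*.

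Annexes 4 and 9 both open by saying that their codes will be reviewed and updated before study initiation. Section 9.3.1 calls the lists preliminary and allows refinement in the SAP.

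**The concern.** Table 3 says that any statin dispensing should establish hyperlipidaemia. The list it names for that purpose leaves out every statin combined with another agent, although Annex 4 of the same protocol recognises those tablets as statins. A patient could be recorded as a prior statin user and as not hyperlipidaemic on the strength of the same dispensing.

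Hyperlipidaemia counts towards the proportion starting tofacitinib with at least one CV factor and adds one point to the summed CV score. Section 9.7.2.4.3 compares both across the CV and malignancy reporting periods. It also helps decide which UC patients enter the maintenance-dose outcomes in Table 3 and Section 9.7.2.5.1. Drug codes matter here because Section 9.9.1.2 says that outpatient diagnoses come only from long-term disease registrations.

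The Annex 4 error runs the other way: one nystatin dispensing would make a patient a prior statin user.

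**Working it through.** No published figure depends on these lists, so the check is a set comparison of the codes as printed.

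| List | Distinct codes | Composition |
|---|---|---|
| Annex 4, Statins | 37 | 8 plain C10AA, 21 C10B, 2 A10BH, 6 non-statins |
| Annex 9 | 47 (C10AB01 is printed twice) | all C10A; no C10B, no A10BH |
| Annex 11, statins | 7 | 6 plain C10AA, 1 C10B (C10BA05) |

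**Step 1: combinations in Annex 4.** The C10B codes by statin are atorvastatin 7, lovastatin 1, pravastatin 2, rosuvastatin 7 and simvastatin 4: 7 + 1 + 2 + 7 + 4 = 21. Adding A10BH51 and A10BH52 (each a gliptin with a statin) gives 23.

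**Step 2: Annex 4 against Annex 9.** All 8 plain statins in Annex 4 are in Annex 9. The other 37 − 8 = 29 codes are not. Of these, 23 are real statin combinations and 6 are non-statins: J01DH51, A07AA02, D01AA01, G01AA01, G01AA51 and L01XX08.

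**Step 3: Annex 11.** Its statin list lacks two of the eight plain statins, C10AA05 (atorvastatin) and C10AA06 (cerivastatin), and 20 of the 21 C10B codes.

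**Step 4: who is missed.** Under Table 3's *or* rule a patient is lost only if all three conditions hold: a fixed statin combination is dispensed, there is no C10A dispensing in the window, and there is no hyperlipidaemia ICD-10 code. Let *q* be the share of initiators in that position and *r* the share of those who have no other CV factor. Then:

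- mean CV score falls by *q* × 1 = *q*;
- proportion with at least one CV factor falls by *q* × *r*;
- the error in a period 3 versus period 1 difference in mean score is −(*q*₃ − *q*₁).

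The protocol gives neither *q* nor *r*, so the size cannot be computed. For scale, the smallest score difference in Table 6 is 0.10. For the list error alone to produce a spurious difference of that size, *q* would have to change by 10 percentage points between periods.

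**Step 5: can the blood-pressure component rescue these patients?** Not through the drug lists. Annex 8 contains only C02 codes, so a patient whose only relevant tablet is atorvastatin with amlodipine and perindopril (C10BX11) matches neither Annex 8 nor Annex 9. A hypertension diagnosis code would still count.

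**Step 6: where the six non-statin codes go.** Annex 4 feeds prior use of statins, a medication-history variable that Section 9.7.1 only describes and tabulates. Hyperlipidaemia uses Annex 9, which contains none of the six, so they cannot reach the CV factor, the CV score or any regression.

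**The case against.** The strongest reply is that the lists are provisional. The protocol says so in Section 9.3.1 and at the head of Annexes 4 and 9, and it requires sponsor review before the study starts. This stands as a limit on the wording: the misclassification would occur if the lists were used unrevised, and has not been shown to have occurred. It does not remove the point. The lists are written out, Table 3 calls them complete, and they disagree with each other. A review of each list on its own could miss the gap between Annexes 4 and 9.

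Other parts of the reply also stand:

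- **Diagnosis route.** A diagnosis code or any plain C10A dispensing rescues the patient, so the loss is smaller than the share using combinations only.
- **Masking.** Age 65 or over, diabetes, hypertension or another listed factor keeps a patient in the at-least-one proportion and in the UC dose outcomes. For the two A10BH products, Annex 11's A10* codes for diabetes may do this at baseline, given enough dispensings. The summed score still loses its point for hyperlipidaemia.
- **Same list throughout.** All reporting periods use the same codes. A reader might infer that the between-period comparisons are biased. The document gives no evidence that combination-only use changes over time, so the main expected effect is on levels.
- **Hospital drugs.** Section 9.9.2 says drugs given in hospital are unavailable unless invoiced separately. Most contamination of prior statin use would then probably come from nystatin, though that rests on general knowledge of where these drugs are used.
- **Annex 11.** A reader might infer a third, contradictory patient classification. Dyslipidaemia is not a separate Table 3 variable, and the *and* can be read as listing code sources. What remains is an ambiguity in the annex that supplies the factor's ICD-10 codes.

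A reader might also want a percentage for either error. Any such figure would rest on assumed dispensing rates for nystatin and for combination-only use, which the document does not give.

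**Conclusion.** The point holds conditionally. If Annex 9 is applied as printed, hyperlipidaemia is under-ascertained in patients treated only with one of 23 omitted statin combinations and lacking a diagnosis code. The CV score falls by one for each such patient. The at-least-one-CV-factor proportion and the UC dose outcomes are affected only where no other qualifying factor is present. The size is unknown, and the effect falls mainly on levels unless combination use shifts between periods.

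The six non-statin codes in Annex 4 are a separate and lesser error, confined to one descriptive row. The stronger reading, that they also distort the CV risk-factor outcomes, is not supported, because those outcomes never use Annex 4's statin list. The differing list and rule in Annex 11 need reconciling.

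The conclusion rests on the printed codes and on Table 3's definitions being applied literally. It assumes nothing about prescribing frequencies. The correction should be made, but no sample-size figure depends on it.

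**What to change.** Before extraction:

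1. **Annex 9:** add the 21 C10BA/C10BX statin combinations from Annex 4, plus A10BH51 and A10BH52. Distinct codes rise from 47 to 47 + 23 = 70.
2. **Annex 4, Statins:** delete J01DH51, A07AA02, D01AA01, G01AA01, G01AA51 and L01XX08. This leaves 37 − 6 = 31 codes.
3. **Annex 11:** keep the ICD-10 codes, replace the separate statin and fibrate codes with a reference to the corrected Annex 9 (which includes C10AA05), and state the same diagnosis *or* dispensing rule as Table 3.

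The cost is an edit to three code lists. It needs no new data source, design change or sample-size revision. The combination codes already stand in Annex 4, so they should be within the planned extraction in any case.

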ANNEX 5. LIST OF DIAGNOSIS CODES FOR SELECT IMMUNODEFICIENCIES OF INTEREST

All codes will be reviewed and updated prior to study initiation.

Immunodeficiency diagnosis description	ICD-10 diagnosis code
Immunodeficiency with predominantly antibody	D80.x
defects	
Combined immunodeficiencies	D81.x
Immunodeficiency associated with other major	D82.x
defects	
Common variable immunodeficiency	D83.x
Other immunodeficiencies	D84.x
Sarcoidosis	D86.x
Other disorders involving the immune mechanism,	D89.x
not elsewhere classified	

ANNEX 6. LIST OF DIAGNOSIS AND PROCEDURE CODES FOR INTERSTITIAL LUNG DISEASE

A majority of the following codes were derived from Curtis et al. (2015).³⁴ All codes will be reviewed and updated prior to study initiation.

ILD diagnosis description	ICD-10 diagnosis code	
Codes in the standard, specific definition of ILD		
Pulmonary fibrosis, unspecified	J841	
Other specified interstitial pulmonary diseases	J848	
Acute interstitial pheumonitis	J841	
Alveolar proteinosis	J840	
Interstitial pulmonary disease, unspecified	J849	
Rheumatoid lung disease with rheumatoid arthritis of	M0510	
unspecified site		

Computed tomography of the thorax

Computerised axial tomography of thorax

Other tomography of thorax

Bronchoscopy, rigid or flexible, including fluoroscopic guidance, when performed; with bronchial or endobronchial biopsy(s), single or multiple sites

Bronchoscopy, rigid or flexible, including fluoroscopic guidance, when performed; with transbronchial lung biopsy(s), single lobe

Bronchoscopy, rigid or flexible, including fluoroscopic guidance, when performed; with transbronchial needle aspiration biopsy(s), trachea, main stem and/or lobar bronchus

Bronchoscopy, rigid or flexible, including fluoroscopic guidance, when performed; with transbronchial lung biopsy(s), each additional lobe

Bronchoscopy, rigid or flexible, including fluoroscopic guidance, when performed; with transbronchial needle aspiration biopsy(s), each additional

Thoracotomy, limited, for biopsy of lung or pleura

Thoracotomy, with diagnostic biopsy of lung infiltrate(s) (e.g., wedge and incisional), unilateral

Thoracotomy, with diagnostic biopsy of lung nodule/mass (e.g., wedge and incisional), unilateral

Thoracotomy, with biopsy(ies) of pleura

Biopsy, pleura; percutaneous needle

Biopsy, lung or mediastinum, percutaneous needle

Thoracoscopy, diagnostic (separate procedure); pericardial sac, with biopsy

Thoracoscopy, diagnostic (separate procedure); mediastinal space, with biopsy

Thoracoscopy; with diagnostic biopsy of lung infiltrate (e.g., wedge and incisional), unilateral

Thoracoscopy; with diagnostic biopsy of lung nodule/mass (e.g., wedge and incisional), unilateral

Thoracoscopy; with biopsy(ies) of pleura

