9.3. Variables

9.3.1. Variables and definitions

Table 3 summarises and defines the study variables to be collected and analysed in SNDS. Unless otherwise specified, these variables will be assessed during each patient's entire study period (baseline period and follow-up period).

This study will use code-based algorithms from the literature and/or other code lists to identify study variables. Published validated algorithms will be used where available.^{6, 7} All code-based algorithms and code lists will be reviewed and/or approved by Pfizer prior to

study initiation. Preliminary algorithms and/or codes are proposed in the following (Table 3); see also Annexes). Final algorithms and/or code lists may be refined as part of the statistical analysis plan (SAP) development. It is also to be noted that while laboratory tests performed are captured, results of laboratory tests are not available in the SNDS database.

Table 3. Operational definitions of study variables in Système National des Données de Santé

Variable	Role	Operational definition
Exposure		
Tofacitinib treatment	Exposure	Defined as having ≥1 ATC code (L04AA29) for a reimbursed prescription of tofacitinib during the indexing period. Index date is defined as the date of the first reimbursed prescription of tofacitinib.
Indication		
Indication	Indication (including off-label use)	Reported in the following categories: RA, PsA, UC and off-label/unknown based on hospital discharge diagnoses and active registration for diagnoses reported in the long-term disease (LTD) database for outpatients in the relevant time period. If there are no diagnosis codes for RA, PsA or UC, it will be categorised as off-label/unknown indications. Details will be further developed in the SAP.
		List of diagnoses codes for indications in ANNEX 13. LIST OF DIAGNOSIS CODES FOR INDICATIONS.
Primary Objective 1: I	Demographics, comorbi	dities and prior and current medications
		T OF CODES FOR COMORBIDITIES, unless otherwise
Age at tofacitinib initiation	Demographic	Calculated as the date of tofacitinib initiation minus the patient's month and year of birth and reported in the following categories: <18 years, 18-29 years and 30-39 years; 40-49 years; 50-59 years; 60-69 years; 70-79 years; ≥80 years; and <65 years and ≥65 years.
Sex	Demographic	Reported in the following categories: Male, Female and Unknown. Assessed on the date of the index tofacitinib prescription dispensing.

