Hepatic impairment	Comorbidity	Defined as ≥1 International Classification of Disease, 10th Revision (ICD-10) diagnosis code for hepatic impairment.
Hepatic impairment, mild or moderate	Comorbidity	Defined as ≥1 ICD-10 diagnosis code for mild or moderate hepatic impairment.
Hepatic impairment, severe	Comorbidity	Defined as ≥1 ICD-10 diagnosis code or procedure code for severe hepatic impairment.
Renal impairment	Comorbidity	Defined as ≥1 ICD-10 diagnosis code or procedure code for renal impairment
Renal impairment, mild	Comorbidity	Defined as ≥1 ICD-10 diagnosis code or procedure code for mild renal impairment
Renal impairment, moderate	Comorbidity	Defined as ≥1 ICD-10 diagnosis code or procedures code for moderate renal impairment
Renal impairment, severe	Comorbidity	Defined as ≥1 ICD-10 diagnosis code or procedure code for severe renal impairment
Herpes zoster (HZ)	Comorbidity	Defined as ≥1 ICD-10 diagnosis code for HZ.

Table 3. Operational definitions of study variables in Système National des Données de Santé

Variable	Role	Operational definition
Human immunodeficiency virus (HIV)	Comorbidity	Defined as ≥1 ICD-10 diagnosis code for HIV.
Tuberculosis (TB), including both active and latent TB	Comorbidity	Defined as ≥1 ICD-10 diagnosis code for TB.
Viral hepatitis B or C	Comorbidity	Defined as ≥1 ICD-10 diagnosis code for viral hepatitis B or C.
Serious and opportunistic infections of interest (including HIV, HZ, TB and viral hepatitis B and C)	Comorbidity	Defined as ≥1 ICD-10 diagnosis code for a serious and/or opportunistic infection of interest. Complete list in ANNEX 3. LIST OF DIAGNOSIS CODES FOR SELECT INFECTIONS OF INTEREST
Diverticulitis	Comorbidity	Defined as ≥1 ICD-10 diagnosis code for diverticulitis.
Malignancy (non- metastatic and metastatic, excluding NMSC)	Comorbidity	Defined as ≥1 ICD-10 diagnosis code for a malignancy (excluding NMSC).
NMSC	Comorbidity	Defined as ≥1 ICD-10 diagnosis code for NMSC.
Gastrointestinal perforation	Comorbidity	Defined as ≥1 ICD-10 diagnosis code for gastrointestinal perforation.
Interstitial lung disease	Comorbidity	Defined as ≥1 ICD-10 diagnosis code for interstitial lung disease. Complete list in ANNEX 6. LIST OF DIAGNOSIS AND PROCEDURE CODES FOR INTERSTITIAL LUNG DISEASE
Diabetes	Comorbidity	Defined as ≥1 ICD-10 diagnosis code for diabetes or ≥3 (or at least 2 in case of large pack sizes) prescription dispensing of oral antidiabetic agents and/or insulin (identified by ATC codes).

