ANNEX 13. LIST OF DIAGNOSIS CODES FOR INDICATIONS

Approved Indication	ICD10 Code	Code Description
Ulcerative colitis	K51	Ulcerative colitis
Rheumatoid arthritis	M05	Rheumatoid arthritis with rheumatoid factor
	M06	Other rheumatoid arthritis
Psoriatic arthritis	L40.5	Arthropathic psoriasis
	L40* (for LTD only)	Psoriasis
	M07.0	Distal interphalangeal psoriatic arthropathy
	M07.1	Arthritis mutilans
	M07.2	Psoriatic spondylitis
	M07.3	Other psoriatic arthropathies
	M07* (for LTD only)	Psoriatic and enteropathic arthropathies

LTD stands for long-term disease registration database

Document Approval Record

Document Name: A3921403_PROTOCOL- FRANCE DUS_V4.0_26FEB2024

Document Title: A3921403_PROTOCOL- FRANCE DUS_V4.0_26FEB2024

Signed By:	Date(GMT)	Signing Capacity
[name]	29-Feb-2024 17:52:13	Final Approval
[name]	03-Mar-2024 17:58:00	EUQPPV Approval

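### Annex 6 picks up rheumatoid lung disease only through one code limited to an unspecified site, and lists 19 procedures that the Table 3 rule for interstitial lung disease does not use

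*Protocol*

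**What the plan says.** **The rule.** Section 9.3.1, Table 3, lists ILD among the comorbidities of primary objective 1: "Defined as ≥1 ICD-10 diagnosis code for interstitial lung disease". The row refers to Annex 6 for the full code list and names no procedure criterion.

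**The list.** Annex 6 is titled "LIST OF DIAGNOSIS AND PROCEDURE CODES FOR INTERSTITIAL LUNG DISEASE". It has six diagnosis rows: J841, J848, J841 again under a second name, J840, J849 ("Interstitial pulmonary disease, unspecified") and M0510. The M0510 row reads "Rheumatoid lung disease with rheumatoid arthritis of" unspecified site. Procedure descriptions follow, beginning with "Computed tomography of the thorax" and going on to bronchoscopic, needle and surgical biopsies. No code stands beside any of them in the text at hand.

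**Related places.** Annex 13 identifies the RA indication from the whole of M05 ("Rheumatoid arthritis with rheumatoid factor") and of M06, with no site restriction. Section 9.9.1.2 says in general terms that comorbidities are identified by algorithms drawing on diagnosis, treatment and procedure data.

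**Status of the lists.** Annex 6 states: "All codes will be reviewed and updated prior to study initiation". Section 9.3.1 adds: "Final algorithms and/or code lists may be refined as part of the statistical analysis plan (SAP) development".

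**The concern.** There are two separate faults in how Annex 6 serves the rule that cites it.

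1. **The rheumatoid-lung entry is narrow on its face.** A label confined to an unspecified site implies that the same disease can be coded at other sites, and none of those codes is listed. The form of lung disease tied by name to RA is thus found only when one particular site value was recorded, unless a general J84 code is also present.
2. **The procedures have no role.** Annex 6 presents them as part of the ILD code list, while the Table 3 rule counts diagnoses only. The protocol does not say whether they are leftovers, a confirmation step or something else.

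At stake is the reported proportion of tofacitinib initiators with ILD, chiefly in the RA/PsA group, and a definition that two programmers should be able to implement identically.

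**Working it through.** The protocol gives no prevalence, precision or sample size for ILD, so there is no stated figure to reproduce. The check is a count of the entries, a comparison of rule with list, and an illustration under labelled assumptions.

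**Step 1: count the Annex 6 entries.**
- Diagnosis rows: 6. Distinct codes: 5 (J840, J841, J848, J849, M0510), because J841 appears twice.
- Codes for rheumatoid lung disease: 1 (M0510).
- Procedure descriptions: 3 tomography + 5 bronchoscopy + 4 thoracotomy + 2 needle biopsy + 5 thoracoscopy = 19.

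**Step 2: apply the Table 3 rule to an RA patient with rheumatoid lung disease.**

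| Codes recorded | Counted as ILD? |
|---|---|
| M0510, with or without a J84 code | Yes |
| M05.1 at another site, plus J840, J841, J848 or J849 | Yes |
| M05.1 at another site, none of those J84 codes | No |

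The third row is the gap. Under Annex 13 that same M05 record would help classify the patient as RA, while under Annex 6 it contributes nothing to ILD.

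**Step 3: compare with how the protocol writes other definitions.**
- Annex 5 takes whole categories (D80.x to D84.x, D86.x, D89.x). Annex 13 gives M05, M06 and M07.0 to M07.3 with no site digit. M0510 is the exception.
- Where procedures count towards a comorbidity, Table 3 says so: severe hepatic impairment and all the renal impairment rows accept a diagnosis or a procedure code. The ILD row does not. The rule is therefore diagnosis-only, and the 19 procedure lines have no function in it.

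**Step 4: find the group affected.** The abstract and section 9.5 project about 8,000 RA or PsA patients and 2,000 UC patients: 8,000 / (8,000 + 2,000) = 80%. RA alone cannot be separated from PsA.

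**Step 5: illustrate the size (assumed values only).** Let p be the true ILD prevalence in the RA/PsA group, and u the share of ILD patients whose only ILD record is an omitted rheumatoid-lung code.

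Observed prevalence = p × (1 − u); patients missed = 8,000 × p × u.

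| p (assumed) | u (assumed) | Observed | Missed of 8,000 |
|---|---|---|---|
| 2% | 10% | 1.8% | 16 |
| 2% | 50% | 1.0% | 80 |
| 5% | 10% | 4.5% | 40 |
| 5% | 50% | 2.5% | 200 |
| 10% | 10% | 9.0% | 80 |
| 10% | 50% | 5.0% | 400 |
| any | 0% | p | 0 |

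Neither p nor u is in the documents. The table shows only that the result runs from no effect to a visible one, depending on a coding habit the protocol does not describe.

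**Step 6: trace where ILD is used.** Section 9.7.1 has the comorbidities described and tabulated. ILD is not among the VTE, CV or malignancy risk factors in Table 3. It is not a contraindicated-use outcome in section 9.7.2.3.1, and it enters no comparison in sections 9.7.2.4 and 9.7.2.5 and no calculation in section 9.5.

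**The case against.** The strongest reply is that the list is openly provisional. Annex 6 promises a review before the study starts, and section 9.3.1 allows refinement in the SAP, which is not at hand. A patient with RA-related ILD is also still counted through any of the four J84 codes, so the loss could be nil. Finally, the procedure lines stand outside the table in the extracted text, so a code column or sub-heading may have been lost in reading the PDF.

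Much of this stands. It keeps the point minor and rules out any claim about the size of the effect. The absence of procedure codes cannot be held against the plan. What remains is a listed code that is too narrow for its purpose, and an annex whose title and content do not match the rule that cites it. A general promise to review codes does not say that either will be changed. Section 9.4 limits extraction to variables relevant to the study, and section 9.6 has the data holder extract to criteria supplied in advance, so whether procedure codes are needed should be settled before then.

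A reader might go further in several ways that the documents do not support:
- **That ILD is misclassified.** Only a possible undercount is shown; it depends on how often site-specific codes appear without a J84 code.
- **That everyone with a chest CT would be recorded as having ILD.** Table 3 excludes this: the ILD row asks for a diagnosis code, while other rows name procedures where they count. The unused lines misclassify nobody.
- **That the cohort is mainly RA.** Only RA and PsA combined are projected.
- **That the repeated J841 matters.** Under a rule of at least one code it changes no result; it is editorial.

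**Conclusion.** The point holds, at minor severity. As written, the Annex 6 list leaves out rheumatoid lung disease coded at any site other than the unspecified one unless the patient also has J840, J841, J848 or J849. ILD may therefore be under-captured in the RA/PsA group, about 80% of projected patients. The documents do not allow the amount to be estimated, and it could be zero. Separately, the 19 procedures in Annex 6 have no place in the diagnosis-only rule of Table 3, and the general statement in section 9.9.1.2 does not give them one.

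The conclusion assumes that the list is applied as written and that rheumatoid lung disease is sometimes recorded at other sites, as the label of M0510 itself suggests. The consequence is confined to one descriptive proportion under primary objective 1.

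**What to change.** 1. In Annex 6, replace M0510 with the whole M05.1 subcategory, all sites included, or give a reason for the restriction. Confirm the coverage of the subcategory in the code review already promised.
2. Keep the diagnosis-only rule for ILD in Table 3.
3. Remove the 19 procedures from Annex 6 and retitle it as a list of diagnosis codes. If a confirmed definition is wanted, state it separately as a sensitivity definition (diagnosis plus procedure) with its CCAM codes.
4. Delete the second J841 row while the annex is open.

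The cost is an edit to one annex and the matching code list. The main definition needs no new data source. Only the optional sensitivity definition would need procedure codes in the extraction request, so that choice should be made before the criteria go to the data holder.
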